## 7.3. ADJUSTMENTS FOR INTERIM ANALYSES AND MULTIPLE ENDPOINTS

No interim analyses are planned and no adjustments will be made for multiple endpoints. Testing for secondary measures is provided as an aid in interpreting study results and no specific claims are being sought based on secondary measures.

## 8. STATISTICAL METHODS AND EVALUATIONS

### 8.1. SUBJECT DISPOSITION AND ACCOUNTABILITY

Summaries of subject disposition information will be provided and will include the number of subjects screened, enrolled and completed overall and by site (FAS population), the

Confidential & Proprietary

number of subjects with data by time point and site (theoretical due), deaths, stem revisions, the expected number (expected) and the number of subjects completing the study (actual and %).

**Table 3: Subject Disposition by screening and enrollment**

	N
Screened	
Enrolled	
Completed	
Total	

## 8.2. DEMOGRAPHIC AND BASELINE CHARACTERISTICS

Demographic characteristics including age at surgery, gender, operated study hip side and bilateral subjects, will be listed. Height and weight at surgery will be listed for all subjects who allowed use of this information. All pre-operative observations will be summarized descriptively. Summaries for demographic characteristics will be provided in total and by femoral stem type.

Additionally, pre-operative outcome information will be listed as frequency table and all “other” outcomes will be listed separately.

All tables are provided in the appendix, chapter **Error! Reference source not found..**

## 8.3. TREATMENT ADMINISTRATION

Implant information of SL-PLUS™ MIA Ti/HA will be summarized descriptively including the operated side (left or right) and use of lateral or standard stem. A graph will show the use of lateral and standard stem per site by gender.

## 8.4. EFFECTIVENESS EVALUATIONS

### 8.4.1. Primary Analysis

If the difference between  $x_1$  and  $x_2$  measured from fluoroscopic images approximately follows a normal distribution, then a two-sided paired T test will be used to test the mean. The test statistic is a t-score defined by the following equation:

$$T = \frac{\bar{D}}{\frac{sd}{\sqrt{N}}}, \text{ where } \bar{D} = N^{-1} \sum_{i=1}^N (x_{i1} - x_{i2}), \text{ and } sd = \sqrt{\sum_{i=1}^N \frac{(x_i - \bar{D})^2}{N-1}} \text{ with } x_i = x_{i1} - x_{i2}; i = 1, \dots, N$$

If the difference does not follow a normal distribution, then the signed rank test will be used to test the hypothesis.

Confidential & Proprietary

## 8.5. SAFETY EVALUATIONS

### 8.5.1. Adverse Events, Serious Adverse Events and Device Deficiency

Definitions for safety reporting are outlined in chapter 8.1 of the study protocol and in chapter 6.7 of this document.

General and local intra- and post-operative observations will be summarized as frequency tables.

An overall summary of AEs will be provided including the number and percent of subjects with any AE, any related (definitely, probably, possible) AE, any severe AE, any severe and related AE, any AE resulting in death, and any AE resulting in removal or revision of component(s).

All AE will be summarized with count and percent, such as:

- Category of AE (medical diagnosis)
- Severity
- Relationship to study device and procedure
- Outcome
- Study participation
- Actions taken (multiple response)
- Seriousness

If the AE is serious (SAE), a frequency table of SAE categories will be provided.

A device deficiency is an inadequacy of a medical device with respect to its identity, quality, durability, reliability, safety or performance. Device deficiencies include malfunctions, use errors, and inadequate labelling.

### 8.5.2. Radiographic Data

There are no radiographic data.

## 8.6. OTHER EVALUATIONS

There are no other evaluations.

## 9. CHANGES TO PLANNED ANALYSES

No changes were made to planned analyses as outlined in the protocol.

## 10. REFERENCES

None.

## 11. LIST OF TABLES

Confidential & Proprietary

## 12. APPENDIX

### 12.1. INCLUSION/EXCLUSION & INFORMED CONSENT

**Table 5: Enrollment Eligibility**

Eligibility criteria	Total N = xx
No	
Yes	
If no, reason	

### 12.2. DEMOGRAPHICS

**Table 6: Age, Height and Weight by Subject**

Variable	Statistic	Total* N = xx
Age at surgery (in years)	N	
	Mean	
	Min	
	Max	
	SD	
	-95% CI	
	+95% CI	
Height	N	

Confidential & Proprietary

(in cm)	Mean	
	Min	
	Max	
	SD	
	-95% CI	
	+95% CI	
Weight (in kg)	N	
	Mean	
	Min	
	Max	
	SD	
	-95% CI	
	+95% CI	
BMI	N	
	Mean	
	Min	
	Max	
	SD	
	-95% CI	
	+95% CI	

**Table 7: Age, Height and Weight by Hip**

Variable	Statistic	Total N = xx
Age at surgery (in years)	N	
	Mean	
	Min	
	Max	
	SD	

Confidential & Proprietary

	-95% CI	
	+95% CI	
Height (in cm)	N	
	Mean	
	Min	
	Max	
	SD	
	-95% CI	
	+95% CI	
Weight (in kg)	N	
	Mean	
	Min	
	Max	
	SD	
	-95% CI	
	+95% CI	
BMI	N	
	Mean	
	Min	
	Max	
	SD	
	-95% CI	
	+95% CI	

**Table 8: Gender**

Gender	Total N = xx (%)
Female	
Male	

Confidential & Proprietary

**Table 9: Study Side**

Study Side	Total N = xx (%)
Left	
Right	

**Table 10: Bilateral Subject Identification**

Contralateral hip enrolled	Total N = xx (%)
No	
Yes	
If yes, Subject ID	

### 12.3. PRE-OPERATIVE ANALYSIS

**Table 11: Preoperative Planning**

	Statistic	Total N = xx
Distance X	Mean	
	Min	
	Max	
	SD	
	-95% CI	
	+95% CI	

Confidential & Proprietary

**Table 12: Planned Stem Size**

Stem Size	Total N = xx (%)
01	
00	
1	
2	
3	
4	
5	
6	
7	

**Table 13: Planned and used Stem Size**

Used Stem Size	Planned Stem Size										Total N = xx (row %)
	01	00	1	2	3	4	5	6	7		
01											
00											
1											
2											
3											
4											
5											
6											
7											
Total N = xx (row %)											

Confidential & Proprietary

**Table 14: Planned Stem Type**

Stem Type	Total N = xx (%)
Standard	
Lateral	

**Table 15: Planned and used Stem Type**

Used Stem Type	Planned Stem Type		
	Standard	Lateral	Total N = xx (row %)
Standard			
Lateral			
Total N = xx (row %)			

**Table 16: Diagnostic Reason for THA**

Reasons for THA	Total N = xx (%)
Osteoarthritis	
Rheumatoid Arthritis	
Post-Traumatic Arthritis	
Avascular Necrosis	
Dysplasia	
Fracture	
Other	
If other, specify	

Confidential & Proprietary

--	--

**Table 17: Dorr Classification of Femoral Bone Type**

Reasons for THA	Total N = xx (%)
Type A	
Type B	
Type C	

#### 12.4. OPERATIVE ANALYSIS

**Table 18: Fluoroscopic images done**

Fluoroscopic images	Total N = xx (%)
No	
Yes	

**Table 19: Surgical Approach I**

Surgical Approach I	Total N = xx (%)
Anterolateral	
Posterolateral	
Anterior	
Other	
If other, specify	

Confidential & Proprietary

**Table 20: Surgical Approach II**

Surgical Approach II	Total N = xx (%)
Standard	
Minimal Invasive	

**Table 21: Type of rasping instrument**

Rasping instrument	Total N = xx (%)
Slap Hammer	
Woodpecker	
Mallet	
Combination	
If combination, specify	

**Table 22: Implanted Components: Femoral Head**

Femoral Head Typ	Total N = xx (%)
Ceramic Ball heads, Biolox delta	
Ceramic Ball heads, Biolox forte	
CoCr femoral head	
Other	
Femoral Head Size	Total N = xx (%)
28	
32	

Confidential & Proprietary

36	

**Table 23: Implanted Components: Acetabular Cup**

Acetabular Cup Type	Total N = xx (%)
R3™ NO HOLE Acetabular Shells	
R3 NO HOLE HA Acetabular Shells	
R3 THREE HOLE Acetabular Shells	
R3 MULTI HOLE Acetabular Shells	
Other	
Acetabular Cup Size	Total N = xx (%)
28	
46	
48	
50	
52	
54	
56	
58	
60	

**Table 24: Implanted Components: Acetabular Liner**

Acetabular Liner Type	Total N = xx (%)
R3™ XLPE Acetabular Liners	

Confidential & Proprietary

SL-PLUS™ MIA Ti/HA femoral hip stem  
 Statistical Analysis Plan  
 Final Version 1.0  
 2017 09 21

R3™ INTL Delta Ceramic Liners	
Other	
Acetabular Liner Size	Total N = xx (%)
28	
32	
36	

**Table 25: Correction of final stem position necessary**

Necessity of correction	Total N = xx (%)
No	
Yes	
If yes, method	
Smaller ball head length	
Larger ball head length	
Removal of stem and enlargement of femoral bed with last trial rasp	
Other method	
If other, specify	

**Table 26: Leg Length Discrepancy**

Leg Length Discrepancy	PreOP N = xx (%)	PostOP N = xx (%)

 CRF: Operative Analysis

None		
Ipsilateral Longer		
Ipsilateral Shorter		
If Ipsilateral Longer/Shorter	PreOP N = xx (%)	PostOP  N = xx (%)
Ipsilateral Longer (mm)	Mean	
	Min	
	Max	
	SD	
	-95% CI	
	+95% CI	
	PreOP N = xx (%)	PostOP  N = xx (%)
Ipsilateral Shorter (mm)	Mean	
	Min	
	Max	
	SD	
	-95% CI	
	+95% CI	

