| Primary Endpoint: | Mean difference between the position of the last trial rasp and the final implant position as measured by an intraoperative fluoroscopic measurement |
| Secondary Endpoints: | Discrepancy of leg length after total hip arthroplasty Intraoperative complications |
| Length of Study: | 3 months enrollment period = total study duration |
| Number of Sites: | up to 4 sites |
| Sample Size: | 40 |
| Inclusion Criteria: | 
Subject:
 
 requires primary THA with the SL-PLUS® MIA Ti/HA femoral hip stem is at least 21 years of age at the time of surgery is skeletally mature in the PI's judgement has consented to participate in the study by signing the Ethics Committee (EC) approved Informed Consent Form (ICF) |
| Exclusion Criteria: | 
Subject:
 
 requires the use of a ceramic-on-ceramic bearing has infections, acute or chronic, local or systemic has severe muscle, nerve or vascular diseases that endanger the respective limb has lack of bone substance or defective bone quality that jeopardizes the stable seating of the prosthesis has any concomitant disease that may jeopardize implant function has a known allergy to study device or one or more of its components requires a revision surgery and has extensive bone defects has diagnosis of an immunosuppressive disorder is pregnant |

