2.2. Secondary Endpoints

The secondary endpoints include a measurement of leg length discrepancy preoperatively and after insertion of the SL-PLUS® MIA Ti/HA femoral hip stem. In addition, intraoperative complications will be collected.

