6.1.1. Assessment 1: Pre-Operative Visit

During the pre-operative visit a standard anterior-posterior (AP) pelvic hip radiograph will be taken.

The AP view should include full pelvic overview. The pre-operative radiograph will be taken for diagnostic purposes and THA planning. The Investigator will analyze the pre-operative radiograph and collect the following information on the appropriate CRF:

- diagnosis for THA
- bone quality according to Dorr et al. [6]
- distance x_1 between the shoulder of the implant and the tip of the greater trochanter, reference Figure 1, measured during preoperative planning

Based on the pre-operative planning, implant sizes planned to be used during THA will be recorded on the CRF. The leg length difference will be measured by the Investigator or designee during the preoperative physical examination. The length of each lower extremity is determined in cm by measuring the distance between the anterior superior iliac spine (ASIS) and the medial malleolus by using a measuring tape with the subject in supine position [7]. Measured distances will be recorded on the appropriate CRF.

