9.2.2. Secondary Endpoint Analysis

Descriptive analyses will be presented for the secondary endpoints of leg length discrepancy and intraoperative complications.

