## 6.6. SECONDARY ENDPOINTS EVALUATIONS

The secondary endpoint analysis of measurement of leg length discrepancy preoperatively and after insertion of the SL-PLUS™ MIA Ti/HA femoral hip stem (and in addition, collecting intraoperative complications) will also be based on full analysis set (FAS) population.

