**Table 27: Patient Length Difference**

Patient ID	lateral / standard	PreOp Leg Length Difference mm	PostOp Leg Length Difference mm

 CRF: Operative Analysis

 CRF: Operative Analysis

Confidential & Proprietary

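### SAP Table 26 summarises the size of leg length discrepancy only within longer and shorter subsets redefined at each time, and the SAP names no all-patient summary and no paired change with SD and 95% CI

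*SAP*

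**What the plan says.** Protocol section 2.2 states: "The secondary endpoints include a measurement of leg length discrepancy preoperatively and after insertion" of the stem. The protocol synopsis words the endpoint as "Discrepancy of leg length after total hip arthroplasty". Protocol section 9.2.2 plans description only: "Descriptive analyses will be presented for the secondary endpoints of leg length discrepancy and intraoperative complications". SAP section 6.6 adds that the analysis "will also be based on full analysis set (FAS) population".

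On measurement, Protocol section 6.1.1 says "The length of each lower extremity is determined in cm", with a tape. Section 6.1.2 repeats the procedure shortly after surgery. Both legs are therefore recorded at both times.

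The specific plan for this endpoint is in two table shells in SAP section 12.4:

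- **Table 26** counts patients with no discrepancy, operated side longer and operated side shorter, pre-op and post-op. Then, under "If Ipsilateral Longer/Shorter", it gives mean, minimum, maximum, SD and 95% CI within the longer group and within the shorter group, in mm.
- **Table 27** lists, for each patient, stem type, "PreOp Leg Length Difference mm" and the matching post-op value.

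SAP section 8.4 contains only the primary analysis, and section 8.6 states that there are no other evaluations.

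**The concern.** Whether a patient falls in the longer or the shorter group is decided by the outcome itself, separately at each time. A patient can be in the shorter group before surgery and in the longer group, or neither, afterwards. A patient with no discrepancy enters neither mean. The pre-op and post-op columns of one row can thus describe different patients, yet they sit side by side with confidence intervals and invite comparison.

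What a reader would want in one line is not specified: the discrepancy over all patients at each time, and how far each patient's discrepancy moved, with its precision. SAP section 7.2 and Protocol section 9.2 call for mean, median, SD, range and, where appropriate, a 95% CI for continuous variables. Table 26 applies these statistics only to the subsets and omits the median. Leg length difference is one of the consequences of stem malposition named in Protocol section 1, so a clear summary is worth having.

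**Working it through.** The documents state no numerical figure for leg length, so there is none to reproduce. The sample size (35, or 40 allowing 12% missing) belongs to the primary endpoint and is not used here, except that 40 is taken as the number of patients.

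**Inputs (assumed, for illustration only).** Signed discrepancy in mm, negative when the operated leg is shorter:

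- Pre-op: 20 patients at -12, 10 at -4, 4 at 0, 6 at +5.
- Post-op: 10 at -4, 10 at 0, 14 at +6, 6 at +9.

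**Step 1: what Table 26 would print.**

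| | Pre-op | Post-op | Shift |
|---|---|---|---|
| None, n | 4 | 10 | |
| Longer, n | 6 | 20 | |
| Longer, mean | 5.0 | (14×6 + 6×9)/20 = 6.9 | +1.9 |
| Shorter, n | 30 | 10 | |
| Shorter, mean | (20×12 + 10×4)/30 = 9.3 | 4.0 | -5.3 |

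**Step 2: all-patient signed mean**, rebuilt as (n longer × mean longer - n shorter × mean shorter)/N.

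- Pre-op: (6×5.0 - 280)/40 = -250/40 = -6.25 mm.
- Post-op: (20×6.9 - 10×4.0)/40 = 98/40 = +2.45 mm.
- Mean change: 2.45 - (-6.25) = +8.7 mm, if the same 40 patients are measured at both times.

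Neither subset shift (+1.9 or -5.3) is the mean change, but the counts and means together do recover it.

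**Step 3: all-patient absolute mean.** Pre-op (280 + 30)/40 = 7.75 mm; post-op (40 + 138)/40 = 4.45 mm. The post-op signed mean (2.45) is smaller because opposite signs cancel, so both measures are informative.

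**Step 4: spread of the change.** Pair the same two sets of values in two ways. Table 26 is identical in both. The half-width of the 95% CI is t(0.975, 39) × SD/√40, with t = 2.023.

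- Lowest pre-op with lowest post-op: changes of 8 (10 patients), 12 (10), 10 (10), 6 (4) and 4 (6). SD 2.7 mm, half-width 0.9 mm, all 40 lengthened.
- Lowest pre-op with highest post-op: changes of 21 (6), 18 (14), 4 (10), -4 (4) and -9 (6). SD 11.2 mm, half-width 3.6 mm, 30 lengthened and 10 shortened.

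Both give a mean of 348/40 = 8.7 mm. Table 26 does not determine the SD or the interval.

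**Step 5: a second assumed scenario.** Take pre-op discrepancy as normal with mean -8 and SD 8, and post-op as normal with mean 0 and SD 6. The shorter mean goes from 10.30 (84% of patients) to 4.79 (50%), a fall of 5.51. The longer mean goes from 4.19 (16%) to 4.78 (50%), a rise of 0.59. The mean change is 8 mm. Rebuilding again works: 0.16×4.19 - 0.84×10.30 = -7.98 pre-op, and about 0 post-op.

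**The case against.** A reader might infer that the planned tables cannot show how leg length changed. The documents do not support that, for four reasons.

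1. Table 26 prints direction counts at both times. If 20 patients were shorter by 10 mm before surgery and 2 afterwards, the shorter mean would stay at 10 mm, but the count row would read 20 and then 2. The net mean change can also be rebuilt, as in Step 2.
2. Table 27 puts both values for each patient in one row, which is readable in a 40-patient series.
3. SAP section 7.1 allows numeric summaries grouped by time point and provides a paired or unpaired t-test for two-group comparisons.
4. No document defines change as the endpoint. The analysis is descriptive, and SAP section 7.3 says no claims rest on secondary measures.

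All four stand, with limits. Rebuilding is hand work, needs the same patients at both times, and never yields the SD or interval of the change. Table 27 is a listing whose headings do not say which direction is positive; if values were entered unsigned, 5 mm short and 5 mm long would look the same. The rules in section 7.1 are general and neither name leg length nor define a signed variable. And even if only the post-op discrepancy matters, Table 26 has no all-patient mean, SD or interval for it.

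It is also tempting to say the direction-specific means should go. That would be a preference. How many legs ended longer, and by how much, is a legitimate description, and a signed mean alone can hide it: in Step 5 the post-op signed mean is 0 while each half of the patients averages about 4.8 mm off.

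**Conclusion.** The point holds as a gap in the table shells. Table 26's subset means and intervals are not a within-patient comparison, and the SAP names no all-patient signed or absolute summary and no paired change with SD and 95% CI. In the two illustrations the subset means move by +0.6 to +1.9 mm (longer) and about -5.3 to -5.5 mm (shorter) when the mean change is 8.0 to 8.7 mm. One identical Table 26 is compatible with an interval half-width for the change from 0.9 to 3.6 mm. These sizes rest on assumed data, since the documents give no leg length values; the structural point does not depend on them. That patients will move between groups is likely but not stated. The effect is confined to the reporting of one descriptive secondary endpoint.

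**What to change.** In SAP Table 26, keep the None/Longer/Shorter counts and the direction-specific rows. Add, for all FAS patients with data:

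- signed discrepancy, operated minus contralateral leg length, in mm (0 if none), pre-op and post-op;
- absolute discrepancy in mm, pre-op and post-op;
- within-patient change in signed discrepancy, post-op minus pre-op, for patients measured at both times.

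Report N, mean, SD, median, range and 95% CI for each. State the same sign convention in Table 27 (positive when the operated leg is longer), and note that lengths recorded in cm are converted to mm.

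This costs only table-shell wording. Both leg lengths are already recorded at both times, so no new data are needed.

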**Table 27: Patient Length Difference**

Patient ID	lateral / standard	PreOp Leg Length Difference mm	PostOp Leg Length Difference mm

 CRF: Operative Analysis

 CRF: Operative Analysis

Confidential & Proprietary

## 12.5. INDEPENDENT IMAGE REVIEW FLUOROSCOPY

**Table 28: Trial rasp analysis**

	Statistic	Trial Rasp Analysis N = xx
Distance X1 (mm)	Mean	
	Min	
	Max	
	SD	
	-95% CI	
	+95% CI	

**Table 29: Implant analysis**

	Statistic	Implant Analysis N = xx
Distance X2 (mm)	Mean	
	Min	
	Max	
	SD	
	-95% CI	
	+95% CI	

**Table 30: Analysis of Distances**

Distance	Mean	Difference	Significance
X1 (Trial Rasp)			
X2 (Implant)			

Confidential & Proprietary

- Graph with Stem Comparison -

## 12.6. DEVICE DEFICIENCY

**Table 31: Device Deficiency related to an AE**

Relation to AE	Total N = xx (%)
No	
Yes	
If no, if intervention not made, could have led to SADE	
No	
Yes	

**Table 32: Timing of Deficiency**

Timing	Total N = xx (%)
Before use	
During procedural use	
After use	

**Table 33: Duration, if inter-operative delay occurred**

Variable	Statistic	Total N = xx
Duration of inter-operative delay (min)	Mean	
	Min	
	Max	
	SD	
	-95% CI	
	+95% CI	

Confidential & Proprietary

**Table 34: List of Deficiency**

Listing

**12.7. ADVERSE EVENT FORM**

**Table 35: List of Adverse Events**

Description of AE	Total N = xx (%)

**Table 36: Duration of resolved events**

Description of AE	Start Date	End Date

**Table 37: Severity**

Severity	Total N = xx (%)
Mild	
Moderate	
Severe	

Confidential & Proprietary

**Table 38: Relationship to study device and procedure**

	to study device	to study procedure
Relationship	Total N = xx (%)	Total N = xx (%)
Unrelated		
Possible		
Definite		

**Table 39: Serious**

Serious	Total N = xx (%)
No	
Yes	
If yes, specify	
Anticipated	
Unanticipated	

**Table 40: Actions Taken**

None	Total N = xx (%)
Yes	
Rest	
Yes	
Medication Therapy	
Yes	
Surgery/Procedure	
Yes	
Removal or revision surgery	
Yes	
Hospitalization or prolonged	

Confidential & Proprietary

Yes	
Other	
Yes	
If other, specify	

**Table 41: Outcome**

Outcome	Total N = xx (%)
Recovered/Resolved	
Resolved with sequelae	
Recovering/Resolving	
Not recovered/Not resolved	
Fatal	
Unknown	

**Table 42: Study participation discontinued due to event**

Participation discontinued	Total N = xx (%)
No	
Yes	

## 12.8. SERIOUS ADVERSE EVENT REPORT FORM

**Table 43: SAE**

Description of SAE	Total N = xx (%)

Confidential & Proprietary

--	--

**Table 44: Hospitalization**

Hospitalization	Total N = xx (%)
Yes	
No	
Admission Date	
Known	
Unknown	
Discharge Date	
Known	
Unknown	

**Table 45: Discharge Date (Duration of hospitalization)**

Discharge Date (Duration in days)	Total N = xx (%)
Mean	
Min	
Max	
SD	
-95% CI	
+95% CI	

**Table 46: Involvement of study region**

Study region	Total N = xx (%)
No	
Yes	

Confidential & Proprietary

## 12.9. END OF STUDY

**Table 47: Screen Failure**

Screen Failure	Total N = xx (%)
No	
Yes	Excluded from analysis.
If yes, reason	

**Table 48: Completion of study**

Completed	Total N = xx (%)
Yes	
No	
If no, reason	
Subject withdrew consent after study treatment	
Subject not able to return	
Subject lost to follow-up after contact attempts were made according to protocol	
Investigator judgement	
Sponsor terminated study	
Subject deceased	

Confidential & Proprietary

**Table 49: Comments**

Comment

Confidential & Proprietary

SL-PLUS™ MIA Ti/HA femoral hip stem  
Statistical Analysis Plan  
Final Version 1.0  
2017 09 21

Page 33 of 33
